| Creatinine OR Measured or calculated creatinine clearance (GFR can also be used in place of creatinine or creatinine clearance) | $\leq 1.5 \times \text{ULN}$ OR $\geq 60 \text{ mL/min}$ for subject with creatinine levels $> 1.5 \times$ institutional ULN Note: Creatinine clearance should be calculated per institutional standard |
| Hepatic | |
| Total bilirubin | $\leq 2 \text{ mg/dL}$, or direct bilirubin $\leq \text{ULN}$ for those with total bilirubin $> 2 \text{ mg/dL}$ |
| AST (SGOT) and ALT (SGPT) | $\leq 5 \times \text{ULN}$ |
| Albumin | $\geq 3.0 \text{ g/dL}$ Note: No albumin supplement (or BCAA) allowed within the last 14 days. |
| Coagulation | |
| International normalized ratio (INR) or PT aPTT | $\leq 1.5 \times \text{ULN}$ unless subject is receiving anticoagulant therapy as long as PT or aPTT is within therapeutic range of intended use of anticoagulants |

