- If the subject is clinically stable, study treatment dosing may be interrupted for up to 12 weeks. Subjects should undergo weekly laboratory tests including: AST, ALT, ALP, Tbil, Dbil, INR, HBsAg, HBV DNA (if detected at the onset of the flare). Obtain anti-HBe, anti-HBs, and HBV DNA levels (if not detected at the onset of the flare) every 2-3 weeks.
- If ALT returns to normal or Grade 1 (if normal at baseline), or to baseline grade (if Grade 2 at baseline) within 12 weeks, and subjects are clinically stable, subjects may restart study treatment. If these conditions are not met, then study treatment should be permanently discontinued.

b. Hepatitis C Recurrence or Flare

Subjects who achieved SVR₁₂ and subjects with ongoing HCV infection are eligible for enrollment. In rare circumstances, HCV subjects who achieve SVR₁₂ may relapse at later time points. Relapse is characterized by detection of HCV RNA, often accompanied by ALT elevations to $>5\times$ ULN. In the absence of hepatic decompensation, ALT/AST elevations are typically isolated (i.e., limited/no elevations of bilirubin/ALP).

Among subjects with uncontrolled hepatitis C, virologic flares are possible. Hepatitis C flares are characterized by rapid elevations of ALT and AST to $>5\times\text{ULN}$ and/or $>3\times$ baseline along with a rise in HCV RNA. ALT elevation to $\geq10\times\text{ULN}$ and a 1 log elevation in HCV RNA level are common. In the absence of hepatic decompensation, ALT/AST elevations are typically isolated (i.e., limited/no elevations of bilirubin/ALP). Laboratory abnormalities secondary to flare or recurrence are typically observed for 3-5 weeks.

Guidelines for subjects with recurrent HCV infection or an HCV flare are described below:

i. Recurrent HCV infection:

If the subject entered the study with an HCV RNA test of “Target not Detected” and has confirmed detectable HCV RNA (2 specimens, 1 week apart), then the subject has experienced a late HCV relapse or a recurrent infection.

- Question the subject about use of injection or inhalation drugs
- At the time of first detection of HCV RNA, send a specimen for HCV genotyping
- Measure AST, ALT, ALP, Tbil, Dbil, and INR weekly
- Measure HCV RNA levels every 2 weeks
- Therapy with HCV anti-viral treatments should be strongly considered.

ii. HCV Flare:

- At the time of first detection of HCV RNA, send a specimen for HCV genotyping
- Measure AST, ALT, ALP, Tbil, Dbil, INR weekly
- Measure HCV RNA levels every 2 weeks

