- Therapy with HCV anti-viral treatments should be strongly considered.

iii. For both recurrent infection and HCV flare: if ALT returns to normal or Grade 1 (if normal at baseline), or to baseline grade (if Grade 2 at baseline) within 12 weeks, and the subjects are clinically stable, subjects may restart study treatment. If these conditions are not met, then study treatment should be permanently discontinued.

c. Immune-related hepatitis

i. Description: Immune-related hepatitis due to study treatment should be suspected if any of the following is seen:

- AST or ALT baseline values are less than $2\times\text{ULN}$, and AST or ALT laboratory values increase to $\geq5\times\text{ULN}$
- Among subjects with baseline ALT or AST $\geq2\times\text{ULN}$, levels increase to $>3\times$ the baseline level

- AST/ALT >500 U/L regardless of baseline level
- Among subjects with baseline Tbil levels <1.5 mg/dL: a value of >2.0 mg/dL
- Among subjects with baseline Tbil levels that are ≥ 1.5 mg/dL: a value of $\geq 2 \times$ the baseline level
- Total bilirubin >3.0 mg/dL regardless of baseline level.

Immune-related hepatitis is a diagnosis made after excluding other possible etiologies for the change. Viral flare (if applicable), biliary or vascular obstruction, infection, medications, and alcohol use must be ruled out (see below).

ii. Management

- Interrupt study treatment and alert the Sponsor as per ECI criteria above for ALT, AST, bilirubin, and hepatic decompensation.
- Start IV corticosteroid (methylprednisolone 125 mg or equivalent) followed by oral corticosteroid.
- Monitor with biweekly laboratory tests including AST, ALT, Tbil, Dbil, ALP, and INR.
- If symptoms and laboratory tests resolve to Grade ≤ 1 or baseline (if abnormal at baseline), taper steroids over 28 days. Study treatment may be restarted after steroid treatment has been tapered to prednisone ≤ 10 mg/day (or equivalent dose of another agent). Treatment and laboratory results must be reported on a case report form (CRF).
- If laboratory abnormalities do not resolve within 3 weeks, or steroids cannot be lowered to ≤ 10 mg/day (or prednisone equivalent) within 12 weeks, or subjects show evidence of decompensation to CP C status or have esophageal or variceal bleeding at any point, treatment must be permanently discontinued. This must be reported on a CRF.

d. Other Hepatic Events of Clinical Interest

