- Infection needs to be ruled out with cultures of blood, urine, and ascites (if possible), as well as chest X-ray and abdominal imaging if relevant. If an infection is found, antibiotics should be started.
- If Tbil is elevated above baseline, imaging should be obtained to rule out vascular compromise, biliary obstruction, and/or tumor progression. If biliary obstruction is present, consultation with a gastroenterologist and/or an interventional radiologist should be obtained to see if the obstruction may be relieved.
- A careful review of drugs, including herbal and alternative medications, should be obtained, and alcohol use should be ruled out. See Section 5.5.2 for drugs which may interfere with hepatic function.

- For all of these cases, subjects may resume study treatment if they are clinically stable after appropriate therapy or discontinue the causative agent, as long as laboratory values have returned to Grade 1 or baseline (if normal or Grade 1 at start) or to baseline grade within 3 weeks.
- Treatment must be permanently discontinued if the subject is off study treatment for infection, obstruction, or drug/alcohol-related toxicity for more than 3 weeks, or if they have esophageal bleeding, or become CP C at any point.

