Laboratory tests for screening should be performed within 7 days prior to the first dose of study treatment. An exception is hepatitis, AFP, and thyroid test, which may be performed within 28 days prior to first dose. Subjects eligible for study retreatment should have imaging performed within 21 days and laboratory tests performed within 7 days prior to the first dose of study treatment in the Second Course Phase. After Cycle 1, in both the Initial Treatment Phase and the Second Course Phase, pre-dose laboratory safety tests can be conducted up to 72 hours prior to dosing unless otherwise noted on the flow charts.

Laboratory test results must be reviewed by the investigator or qualified designee and found to be acceptable prior to administration of each dose of trial treatment, unless otherwise specified in the flow chart. Unresolved abnormal laboratory values that are drug-related AEs should be followed until resolution. Laboratory tests do not need to be repeated after the end of treatment if laboratory results are within normal range.

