7.1.6.2 Treatment Period

Visit requirements are outlined in the Trial Flow Chart (Section 6.0). Specific procedure-related details are provided above in Trial Procedures (Section 7.0).

Subjects who stop study drug with SD or better may be eligible for up to 17 additional trial treatments (approximately 1 year) if they progress after stopping study treatments. Retreatment with study drug is termed the Second Course Phase and is only available if the trial remains open and the subject meets the following conditions:

- **Either**
 - Stopped initial treatment with study treatment after attaining an investigator-determined CR according to RECIST 1.1
 - Was treated with at least 8 trial treatments (approximately 6 months) before discontinuing therapy
 - Received at least two study treatments beyond the date when the initial CR was declared

OR

- Had stable disease (SD), PR or CR and stopped study treatment after 35 treatments (approximately 2 years) for reasons other than disease progression or intolerance

- **AND**
 - Experienced an investigator-determined confirmed radiographic disease progression after stopping their initial study treatment
 - Did not receive any anti-cancer treatment since the last dose of study treatment
 - Has a performance status of 0 or 1 on the ECOG Performance Scale
 - Demonstrates adequate organ function as detailed in Section 5.1.2
 - Female subject of childbearing potential should have a negative serum or urine pregnancy test within 72 hours prior to receiving retreatment with study medication (Cycle 1, Day 1).

- Female subjects of childbearing potential must be willing to use an adequate method of contraception as outlined in Section 5.7.2 – Contraception, starting with the first dose of study medication through at least 120 days or longer based on local regulation, after the last dose of study medication.
 - *Note: Abstinence is acceptable if this is the usual lifestyle and preferred contraception for the subject.*
- Male subjects of child bearing potential must agree to use an adequate method of contraception as outlined in Section 5.7.2 – Contraception, and not to donate sperm starting with the first dose of study therapy through at least 120 days or longer based on local regulation, after the last dose of study therapy.
 - *Note: Abstinence is acceptable if this is the usual lifestyle and preferred contraception for the subject.*

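### The restart rule after a hepatitis B or C flare omits Grade 1 baseline ALT, so a subject who recovers to that baseline is, read literally, permanently stopped

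*Combined protocol and SAP*

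**What the plan says.** Section 5.2.1.3, part a (Hepatitis B Flare), allows dosing to be interrupted for up to 12 weeks. It then permits restart in a clinically stable subject "If ALT returns to normal or Grade 1 (if normal at baseline), or to baseline grade (if Grade 2 at baseline) within 12 weeks". The sentence after that sets the default: "If these conditions are not met, then study treatment should be permanently discontinued". Part b.iii, which covers both recurrent hepatitis C infection and hepatitis C flare, uses the same test ("if ALT returns to normal or Grade 1 (if normal at baseline), or to baseline grade (if Grade 2 at baseline) within 12 weeks"), followed by the same default.

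The other two hepatic restart rules in the section are worded differently:

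- Part c (immune-related hepatitis): "If symptoms and laboratory tests resolve to Grade ≤ 1 or baseline (if abnormal at baseline), taper steroids over 28 days". Restart follows once the steroid dose is low enough.
- Part d (other hepatic events): subjects may resume if stable and "laboratory values have returned to Grade 1 or baseline (if normal or Grade 1 at start) or to baseline grade within 3 weeks".

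Table 1 in Section 5.1.2 admits subjects with AST and ALT up to 5 x ULN, so raised baseline ALT is compatible with entry.

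**The concern.** The flare rule sets an ALT target for two baseline groups, normal and Grade 2, and skips the group between them. Because the default is a permanent stop, the gap has a consequence. A subject with Grade 1 ALT at entry who flares and recovers fully to that entry level does not satisfy the sentence. A subject with worse ALT at entry who recovers to that worse level does. The plan gives no safety reason for being stricter with the middle group than with the groups on either side.

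The stop is hard to undo. Under Section 7.1.6.2 a second course is open only to subjects who stopped after a complete response (with minimum treatment requirements) or who "stopped study treatment after 35 treatments (approximately 2 years) for reasons other than disease progression or intolerance". A subject stopped at a flare before either point has no stated route back, in a setting where Section 4.1.4 says there is no standard second-line therapy. Sites may also diverge, some applying the words as written and others the apparent intent of recovery to baseline, so that like subjects are treated differently.

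**Working it through.** No sample size, power or alpha figure is involved. The check is a reading of the rule, case by case.

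**Step 1: is a Grade 1 baseline possible?** Yes. Table 1 allows ALT up to 5 x ULN, and the flare rule itself provides for Grade 2 entrants, so the milder Grade 1 is also eligible.

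**Step 2: parse the sentence both ways.**

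- *Reading A: the first parenthesis governs both normal and Grade 1 as targets.* A Grade 1 entrant has no target. The restart condition cannot be met, whatever the recovery.
- *Reading B: the parenthesis governs only Grade 1 as a target.* A Grade 1 entrant must reach normal, which is better than his or her own baseline. Recovery to Grade 1 is not enough.

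The readings differ for a Grade 1 entrant who normalises (stopped under A, may restart under B). They agree for one who recovers to Grade 1: condition not met, permanent stop.

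**Step 3: compare the four rules.** Take a clinically stable subject whose ALT returns to the baseline grade within the time limit.

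| Rule in 5.2.1.3 | Baseline normal | Baseline Grade 1 | Baseline Grade 2 |
|---|---|---|---|
| a. Hepatitis B flare | restart | **stop** | restart |
| b.iii Hepatitis C recurrence or flare | restart | **stop** | restart |
| c. Immune-related hepatitis | met | met | met |
| d. Other hepatic events | met | met | met |

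That is 4 x 3 = 12 combinations: 10 meet the ALT condition and 2 do not. Both failures are Grade 1 at baseline, and they occur under both readings. For part c, *met* refers to the laboratory condition only, since restart there also needs prednisone tapered to 10 mg/day or less. Parts c and d govern other diagnoses, and part d has a 3-week window rather than 12, so neither supplies the missing branch for a flare.

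**Step 4: an example using the hold thresholds at the start of 5.2.1.3.**

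- X: baseline 1.5 x ULN (below 2 x ULN), held at 5 x ULN or more, returns to 1.5 x ULN. Stopped.
- Y: baseline 4 x ULN (at least 2 x ULN), held above 3 x 4 = 12 x ULN (or above 500 U/L), returns to 4 x ULN. May restart, with ALT 4 - 1.5 = 2.5 x ULN higher than X.
- Z: baseline normal, returns to 1.5 x ULN. May restart, at the same ALT as X.

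The documents name CTCAE version 4.0 but do not print its ALT cut-offs. The example therefore assumes that 1.5 x ULN is above normal and within Grade 1, and that 4 x ULN is within Grade 2. It works for any Grade 1/Grade 2 border from 1.5 to below 4 x ULN, provided Grade 2 extends to at least 4 x ULN. Steps 1 to 3 do not need this assumption.

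**The case against.** The strongest reply is that the sentence is silent about Grade 1 entrants and does not condemn them. If no target was set for them, the closing sentence can be taken to address only subjects for whom one was set. The evident intent is recovery to about baseline, and a sensible investigator would restart. The surroundings support this: the section is headed as guidance and says *should*; a hepatologist is to be consulted on hepatitis B flare care; the Sponsor is told of every hepatic event of clinical interest within 24 hours, and every retreatment and permanent discontinuation must be reported to it; and the mandatory discontinuation list in 5.8.1 has no item specific to incomplete ALT recovery after a flare.

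These points make an unnoticed literal stop less likely, and that part stands. None of them provides another restart criterion. Permission to restart is conditional, the stated alternative is a permanent stop, and Reading B leads to that stop without any appeal to silence.

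The path is also narrow. Hepatitis B subjects are capped at about 30% of the trial (about 122), treated ones must have a controlled viral load at entry, and late hepatitis C relapse is described as rare. The subject must also enter at Grade 1, flare, remain stable and recover to Grade 1 but not to normal. This is fair, and it limits the reach. The 12-combination count describes the text and not patients.

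Nor is there a trial-level effect to point to: efficacy is analysed by ITT, and subjects who stop treatment remain in follow-up. It is also true that this is better called a drafting omission than a choice of design.

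**Conclusion.** The concern holds: the rule is wrong as written and small in reach. A stable, eligible subject with Grade 1 baseline ALT who recovers to Grade 1 after a hepatitis B or C flare fails the stated restart condition under either reading. Subjects on both sides of that baseline may restart.

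How many subjects this touches cannot be estimated, because the documents give no baseline ALT distribution, no flare rate and no share recovering to Grade 1 but not to normal. No bias in the PFS or OS analyses is claimed, since the rule is applied blinded to both arms. Nor does the conclusion imply that dosing may resume while an AST or bilirubin hold criterion is still met. That hold remains, as does the requirement in 7.1.3.1 that laboratory results be "found to be acceptable prior to administration of each dose of trial treatment, unless otherwise specified in the flow chart". The correction should be made because the literal result is a wrong and hard-to-reverse treatment decision for an individual.

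**What to change.** In Section 5.2.1.3, parts a and b.iii, extend the first parenthesis to read *if normal or Grade 1 at baseline*, and leave the Grade 2 branch, the 12-week limit and the clinical-stability requirement as they are. Part d already frames its condition this way. The change accepts no ALT level that the rule does not already accept for a normal-baseline subject.

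Optionally, add a pointer that the hold criteria at the start of 5.2.1.3 and the pre-dose laboratory review in 7.1.3.1 still apply at restart, since ALT is the only laboratory value the sentence names.

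The cost is three added words in two places, by clarification letter or at the next amendment. No new tests are needed: ALT is already measured weekly during hepatitis B flare and during hepatitis C recurrence or flare.

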5.2.2 Timing of Dose Administration

Cycle 1, Day 1 treatment with study drug should begin on the day of randomization, but no later than 3 days from the date the subject is randomized to study treatment. However, every effort should be made to begin trial treatment on the day of randomization.

For all additional cycles of study treatment, treatment may be administered up to 3 days before or 3 days after the scheduled Day 1 of each cycle due to administrative reasons per the investigator's judgment.

All study treatments will begin on Day 1 of each cycle after all pre-dose study procedures and assessments have been completed as detailed on the Trial Flow Chart –Section 6.0

Study treatment will be administered as a 30 minute IV infusion every 3 weeks. Sites should make every effort to target infusion timing to be as close to 30 minutes as possible. However, given the variability of infusion pumps from site to site, a window of -5 min and +10 min is permitted (i.e., infusion time is 30 minutes: -5 min/+10 min).

The Pharmacy Manual contains specific instructions for the preparation of the study treatment infusion fluid and administration of infusion solution.

All trial treatments will be administered on an outpatient basis.

5.2.3 Trial Blinding

A double-blinding technique with in-house blinding will be used. Pembrolizumab and placebo will be packaged identically by the site pharmacy so that the blind is maintained. The subject, the investigator and Sponsor personnel or delegate(s) who are involved in the treatment or clinical evaluation of the subjects are unaware of the group assignments.

See Section 7.1.5.2, Blinding/Unblinding, for a description of the method of unblinding a subject during the trial, should such action be warranted.

5.3 Randomization

Treatment allocation/randomization will occur centrally using an interactive voice response system / integrated web response system (IVRS/IWRS). There are 2 treatment arms. Subjects will be assigned randomly in a 2:1 ratio to pembrolizumab and placebo, respectively.

5.4 Stratification

Treatment allocation/randomization will be stratified according to the following factors:

1. Geographic region (Asia without Japan, Non-Asia with Japan)
2. Macrovascular invasion (Yes, No)
3. α -Fetoprotein (ng/mL) (<200, \geq 200)

5.5 Concomitant Medications/Vaccinations (Allowed & Prohibited)

Medications or vaccinations specifically prohibited in the exclusion criteria are not allowed during the ongoing trial. If there is a clinical indication for any medication or vaccination specifically prohibited during the trial, discontinuation from trial therapy or vaccination may be required. The investigator should discuss any questions regarding this with the Sponsor Clinical Director. The final decision on any supportive therapy or vaccination rests with the investigator and/or the subject's primary physician. However, the decision to continue the subject on trial therapy or vaccination schedule requires the mutual agreement of the investigator, the Sponsor and the subject.

5.5.1 Acceptable Concomitant Medications

All treatments that the investigator considers necessary for a subject's welfare may be administered at the discretion of the investigator in keeping with the community standards of medical care. All concomitant medication will be recorded on the CRF including all prescription, over-the-counter (OTC), and IV medications and fluids. If changes occur during the trial period, documentation of drug dosage, frequency, route, and date should be included on the CRF.

Palliative and supportive care is permitted during the course of the trial for underlying medical conditions and management of symptoms. Surgery for tumor control or symptom management is not permitted during the study. Palliative radiotherapy is permitted to a single lesion if considered medically necessary by the treating physician as long as the lesion is NOT a RECIST 1.1 defined target lesion and is NOT administered for tumor control. Trial therapy should be held during the course of palliative radiotherapy and should be resumed no earlier than the next scheduled administration of trial therapy. The specifics of the radiation treatment, including the location, will be recorded on the CRF.

All medications received within 30 days before the first dose of trial treatment and within 30 days after the last dose of trial treatment should be recorded. Medications administered more than 30 days after the last dose of trial treatment should be recorded for SAEs and events of clinical interest (ECIs) as defined in Section 7.2.3.

